238 The main research centres involved in the study are:

- 239 • Melbourne School of Population Health, University of Melbourne (managing institution)
- 240 • Kirby Institute, University of New South Wales
- 241 • Department of General Practice, University of Melbourne
- 242 • Institute of Social and Preventive Medicine, University of Bern

243 ***Contact details***

244 Associate [name]
245 Melbourne School of Population Health
246 University of Melbourne
247 [name]
248 [name]
249 [contact]
250 Email: [contact]

251 ***Aims and Objectives***

252 The study is a trial of the effectiveness of an intensive multifaceted intervention to increase rates of
253 annual chlamydia testing in primary care clinics (general practice clinics and AMSs). The hypothesis is
254 that by increasing testing rates to 30% of men and women aged 16 to 29 years, prevalence in clinic

255 attenders will decrease from about 4% to 2% in this population by the end of the trial period by the
256 end of the trial period.

257 ***Primary objective***

- 258 ● To determine whether an intervention to deliver organised regular chlamydia testing for
259 women and men aged 16 to 29 years who have ever had sex attending primary care clinics
260 (general practices and AMSs) leads to a reduction in estimated chlamydia prevalence in 16–
261 29-year old primary care attendees when compared with usual care.

262 ***Secondary objectives***

- 263 ● To determine whether an intervention to deliver organised regular chlamydia testing in
264 primary care clinics (general practices and AMSs) leads to a reduction in the incidence of PID
265 in 16–29-year old primary care attendees.
- 266 ● To determine whether an intervention to deliver organised regular chlamydia testing in
267 primary care clinics (general practices and AMSs) leads to a reduction in the incidence of
268 epididymitis in 16–29-year old primary care attendees.
- 269 ● To determine whether an intervention to deliver organised regular chlamydia testing in
270 primary care clinics (general practices and AMSs) can increase chlamydia testing rates.
- 271 ● To determine the proportion of individuals tested who return for a repeat test 12 months
272 after a previous negative test result.
- 273 ● To determine the proportion of individuals tested who return for a repeat test three months
274 after a positive chlamydia test result.

275 ***Design***

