301 There are inclusion and exclusion criteria at the level of the cluster, the primary care clinic,
302 healthcare professionals and individual patients.

303 ***Clusters***

304 **Inclusion criteria**

- 305 • Rural areas (postcodes) in the Australian States of New South Wales, Victoria, Queensland
306 and South Australia.
- 307 • A minimum population size of five hundred 15 to 29 year olds, as determined by the 2006
308 census data from the Australian Bureau of Statistics.
- 309 • Up to six general practice clinics.

310 **Exclusion criteria**

- 311 • Postcodes with army bases, mining towns, holiday towns or towns with intensive chlamydia
312 control activities.
- 313 • Postcodes with seven or more general practice clinics.
- 314 • Postcodes where one or more clinics refuse to participate in the trial.

315 ***General practice clinics and Aboriginal Medical Services (AMSs)***

316 All general practice clinics and AMSs (irrespective of size) within a cluster will be invited to
317 participate.

318 **Inclusion criteria**

- 319 • Over 75% of GPs working at the clinic must consent to participate in the trial.

320 **Exclusion criteria**

- 321 • None.

322 ***General practitioners and practice nurses***

323 General practitioners (GPs) and practice nurses (PNs) in clinics within eligible clusters will be invited
324 to participate. Consenting GPs and PNs will be recruited prior to the baseline prevalence survey, and
325 newly employed GPs and PNs at participating clinics will be recruited during the trial.

326 **Inclusion criteria**

- 327 • GPs and PNs (fully qualified, locum, and in training) working at participating general practice
328 clinics or AMSs.

329 **Exclusion criteria**

- 330 • None.

331 ***Individuals during the intervention period***

332 GPs will assess the eligibility of patients for chlamydia testing during a clinical consultation.

333 **Inclusion criteria**

- 334 • Men and women aged 16 to 29 years of age who have ever had vaginal or anal sex will be
335 targeted for annual chlamydia testing when they attend a participating clinic for any reason
336 during the trial.

337 **Exclusion criteria**

- 338 • None

339 ***Individuals enrolled in the baseline and final prevalence survey***

340 Research staff will assess eligibility.

341 **Inclusion criteria**

- 342 • Male and female patients aged 16–29 years attending a clinic for consultation with a GP.
343 • Ever had vaginal or anal sexual intercourse.

344 **Exclusion criteria**

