488 reporting text in the medical records. STI test results associated with the epididymitis diagnosis will
489 be extracted and linked with the epididymitis diagnosis.

490 **Testing uptake rates**

491 Testing uptake per year (with 95% CI) of eligible patients will be assessed in intervention and control
492 groups as an overall measure, as well as stratified by sex, age group (16 to 19, 20 to 24, 25 to 29
493 years) and Aboriginal and/or Torres Strait Islander status. The numerator will be the number of
494 individuals aged 16 to 29 years who were tested for chlamydia at least once in the past year; the
495 denominator will be the number of unique individuals aged 16 to 29 years who had a consultation
496 with a GP at the clinic in the past year. The denominator will include patients who have not had
497 sexual intercourse, as this information is not recorded on patient records. The Australian Study of
498 Health and Relationships [87] or similar up-to-date data will be used to adjust denominators for the
499 proportion likely to be sexually active.

500 **Annual re-testing rate**

501 Overall annual re-testing of eligible patients will be determined in intervention and control clusters,
502 and stratified by sex, age group (16 to 19, 20 to 24, 25 to 29 years) and Aboriginal and/or Torres
503 Strait Islander status. The numerator will be the number of individuals aged 16 to 29 years who were
504 tested for chlamydia 12 months (allowable range 10 to 15 months) after a previous chlamydia test;
505 the denominator will be the number of unique individuals aged 16 to 29 years who had at least one

506 chlamydia test in the previous year. The Australian Study of Health and Relationships [87] or similar
507 up-to-date data will be used to adjust denominators for the proportion likely to be sexually active.

508 **Test for repeat infection**

509 Tests for repeat infection in eligible patients following a positive chlamydia diagnosis will be
510 measured overall in intervention and control clusters, and stratified by sex, age group (16 to 19, 20
511 to 24, 25 to 29 years) and Aboriginal and/or Torres Strait Islander status. The numerator will be the
512 number of individuals aged 16 to 29 years re-tested for chlamydia three months (allowable range six
513 weeks to six months) after a positive test; the denominator will be the number of unique individuals
514 aged 16 to 29 years who tested positive for chlamydia in the previous year.

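### The annual re-testing rate adjusts for sexual activity a denominator that holds only people already tested, which inflates the absolute rates

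*Protocol*

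**What the plan says.** All references are to the Protocol.

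- **Testing uptake rates (Secondary endpoints).** The denominator is every 16–29-year-old with a GP consultation in the year. The reason for adjusting it is given there: "The denominator will include patients who have not had" "sexual intercourse, as this information is not recorded on patient records". Survey data on sexual activity are then to correct it.
- **Annual re-testing rate (Secondary endpoints).** The numerator is people "tested for chlamydia 12 months (allowable range 10 to 15 months) after a previous chlamydia test". For the rate's base, "the denominator will be the number of unique individuals aged 16 to 29 years who had at least one" "chlamydia test in the previous year. The Australian Study of Health and Relationships [87] or similar" "up-to-date data will be used to adjust denominators for the proportion likely to be sexually active". No reason for the adjustment is given here.
- **Test for repeat infection (Secondary endpoints).** The denominator is people who tested positive in the previous year, so it too is conditional on a test. It carries no sexual-activity adjustment.
- **Inclusion criteria, individuals during the intervention period.** "Men and women aged 16 to 29 years of age who have ever had vaginal or anal sex will be" targeted for annual testing.
- **Secondary objectives.** The matching objective is the proportion of tested individuals who come back at 12 months "after a previous negative test result".

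**The concern.** The adjustment repairs a particular defect: an all-attender denominator contains people who have never had sex and so were never eligible for a test. A denominator of people already tested does not have that defect, or has it only to a trivial degree, because being tested has already done the selecting. Shrinking it by a general-population share removes people a second time, while the numerator is left alone.

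The quantity at stake is the one that the objective names, an absolute proportion of tested people who return. If the rule is followed, that proportion is reported too high in both arms and the absolute difference between arms is stretched by the same factor.

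A smaller mismatch sits in the same endpoint. The objective concerns re-testing after a negative result, but the numerator accepts any previous test. Under the intervention's reminder system, people who test positive are recalled at three months and people who test negative at 12 months, so the endpoint mixes two recall schedules.

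**Working it through.** **Inputs.** The definitions come from the sections above. The Protocol states neither an expected annual re-testing rate nor a sexually active share, so there is no figure of its own to reproduce. The values of s and of the true rates below are assumptions for illustration.

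**Formula.** Let T be the number tested in the previous year, R the number of them re-tested in the window, s the external sexually active share, and q the sexually experienced share among those tested.

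- Rate as the rule is written: R/(T × s) = (1/s) × (R/T).
- Rate among the sexually experienced tested, taking everyone re-tested to be sexually experienced: R/(T × q).
- Inflation: q/s. It is upward whenever s is below q. Because testing is aimed at people who have ever had sex, q should be close to 1, and the inflation is then about 1/s.

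**Why the correction works for uptake and not for re-testing.** Take 1000 attenders with s = 0.60, 20% of the sexually experienced tested, and 25% of those re-tested.

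- Sexually experienced: 1000 × 0.60 = 600. Tested: 600 × 0.20 = 120. Re-tested: 120 × 0.25 = 30.
- Uptake unadjusted: 120/1000 = 12.0%. Adjusted: 120/(1000 × 0.60) = 20.0%, which is the true figure.
- Re-testing unadjusted: 30/120 = 25.0%, which is the true figure. Adjusted: 30/(120 × 0.60) = 30/72 = 41.7%.

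**Size over a range of s**, with assumed true rates of 30% and 20% in the two arms and the same s in both:

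| s | 1/s | 30% reported as | 20% reported as | Difference (points) | Rate ratio | Odds ratio |
|---|---|---|---|---|---|---|
| no adjustment | 1.00 | 30.0% | 20.0% | 10.0 | 1.50 | 1.71 |
| 0.95 | 1.05 | 31.6% | 21.1% | 10.5 | 1.50 | 1.73 |
| 0.80 | 1.25 | 37.5% | 25.0% | 12.5 | 1.50 | 1.80 |
| 0.60 | 1.67 | 50.0% | 33.3% | 16.7 | 1.50 | 2.00 |

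The odds ratio moves only if it is computed from the scaled proportions.

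**Age strata.** Suppose the true rate is 20% in every age group. Assumed age-specific shares of 0.60, 0.90 and 0.97 would report 33.3% (16–19), 22.2% (20–24) and 20.6% (25–29). One overall share would scale all three groups equally and leave no gradient.

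**Negative versus any index test.** If a fraction p of index tests is positive, the endpoint as written differs from the rate after a negative test by p × (rate after a positive − rate after a negative). Aims and Objectives puts prevalence in attenders at about 4%. Taking p = 0.04 as an assumption, a gap of 30 points between the two rates would shift the result by 0.04 × 30 = 1.2 points, and the shift could never exceed 4 points. Positivity among people chosen for testing may be higher than 4%, in which case the limit rises in proportion.

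**The case against.** The strongest reply is that little depends on this endpoint. It is a process measure that the Summary does not list among the secondary outcomes, and the primary endpoint, the sample size and the PID and epididymitis endpoints do not use it. A share common to both arms cancels from the rate ratio. The Statistical tests section leaves the comparison to suitable hierarchical models, and a person-level binary model would probably not use a scaled denominator at all. All of this stands. It limits the harm mainly to reported rates and absolute differences, but it does not make the rule right.

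Nor can the point be left as detail for a separate analysis plan. The Protocol does not stay silent; it fixes an adjustment, and that adjustment is wrong for this denominator.

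A reader might go further in three ways that the document does not support:

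- **That the youngest group is inflated most.** This needs age-specific shares that are lowest at 16–19. The Protocol does not say that the adjustment is age-specific.
- **That rates could exceed 100%.** This needs a true rate above s, for example above 60% at s = 0.60. The only re-testing figures in the Protocol (Rationale for the trial) are 26.4% in general practice after a positive test and 8.6% to 17.8% at sexual health services. They describe other settings or intervals, but they make such a rate remote.
- **That the endpoint also needs a minimum follow-up of 15 months to match its window.** No defect shown here calls for that. Patients can change clinics at any time (Design), so a rule that required continued attendance could itself select people likelier to be re-tested.

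**Conclusion.** The point holds, at moderate severity. The sexual-activity adjustment is justified for testing uptake and misapplied to annual re-testing. Followed as written, it inflates absolute re-testing rates and absolute arm differences by about 1/s.

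The direction rests only on s being below the sexually experienced share among those tested, which the eligibility rule for testing makes very likely. The size rests on s, which the Protocol does not give. At s = 0.95 the effect is minor and at s = 0.60 it is large, and nothing in the document favours either end. The result should not be read as a bias in the relative comparison of arms when both use one share, nor as touching the primary endpoint.

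The mismatch between a negative index test and any index test is real but secondary, and probably small because positives are likely to be few.

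**What to change.** Delete the adjustment sentence from the annual re-testing endpoint and keep it under testing uptake. The re-testing rate is then simply R/T. This needs no new data and costs one sentence. Reported re-testing rates will be lower than the current rule would give.

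Secondly, align the index test with the objective by restricting both numerator and denominator to people whose index test was negative. If any previous test is really intended, reword the objective instead. Restricting the index test means rewording the two definitions and linking each index result to its re-test. The main extraction tool carries a unique patient code and collects test results, so this should be feasible wherever it is installed.

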225 Guidelines also recommend that a repeat test be performed 3 months after a positive chlamydia
226 diagnosis, yet rates of repeat testing are low. An audit of repeat testing at 25 Australian general
227 practice clinics in 2008–2009 found that only 26.4% of 16–29-year-olds diagnosed with chlamydia
228 were re-tested within 1.5–4 months following a positive chlamydia test [81]. Rates of repeat testing
229 at sexual health services in Australia between 2004 and 2007 were found to be even lower: 8.6% in
230 men who have sex with men (MSM), 11.9% in heterosexual males and 17.8% in heterosexual
231 females [60]. Low repeat testing rates have also been reported in the USA [82].

232 This trial is designed to address the gap in evidence about the effectiveness of an organised program
233 of annual chlamydia testing in young general practice attendees. Its strengths are its cluster
234 randomised design, biological endpoints and multiple rounds of testing.

235

236 ***Principal investigators – ACCEPt Consortium***

Name	Institution
Associate [name]	Melbourne School of Population Health University of Melbourne
[name]	Melbourne School of Population Health University of Melbourne
[name]	Department of General Practice University of Melbourne
[name]	Kirby Institute University of New South Wales
[name]	Kirby Institute University of New South Wales
[name]	Institute of Social and Preventive Medicine, University of Bern
Associate [name]	Kirby Institute University of New South Wales
[name]	Kirby Institute University of New South Wales
Associate [name]	Department of General Practice University of Melbourne
[name]	Kirby Institute University of New South Wales
Associate [name]	Kirby Institute University of New South Wales
[name]	Baker IDI Heart and Diabetes Institute
Associate [name]	Africa Centre for Health and Population Studies University of KwaZulu-Natal
[name]	Health Economics Unit Deakin University
[name]	Australian Research Centre in Sex, Health in Society La Trobe University
Associate [name]	Australian Research Centre in Sex, Health in Society

	La Trobe University
Associate [name]	Victorian Cytology Service
Associate [name]	Victorian Cervical Cytology Registry
Associate [name]	Department of General Practice University of Melbourne
Associate [name]	Department of General Practice University of Melbourne
Associate [name]	Royal Women’s Hospital
Associate [name]	Melbourne Sexual Health Centre
[name]	Burnet Institute

237 ***Main centres***

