- 345 • Language barrier, intoxication, incapacitation (e.g. severe illness), intellectual difficulty, or
346 other circumstances that hinder a patient’s ability to give informed consent.

347 ***Intervention***

348 ***Multifaceted chlamydia screening intervention***

349 The intervention is an organised programme for the delivery of annual chlamydia testing and
350 treatment in general practices and AMSs in Australia. Clinics will receive a multifaceted intervention
351 package that will encourage staff to offer chlamydia testing to all eligible patients in the target
352 population. The intervention package has been designed to be delivered and evaluated as a whole,
353 with the logistics of implementation tailored to the needs and resources of each clinic. The
354 components of the intervention package include:

- 355 • Chlamydia and PID education package for GPs and other clinic staff. This provides a number
356 of strategies for introducing chlamydia testing during a consultation; health education and
357 promotion materials for health care providers and patients; guidelines to facilitate the
358 consistent application of clinical criteria for the diagnosis of PID and epididymitis; and
359 information on effective partner notification.

- 360 • A computer alert programmed into the practice patient management system or as part of a
361 separate consulting sidebar tool (www.racgp.org.au/what-is-sidebar/), prompting
362 GPs or other clinic staff to discuss chlamydia testing with eligible patients.
- 363 • A patient reminder system within the practice patient management system that will recall
364 tested patients via letter, phone or SMS after 12 months if chlamydia negative and after
365 three months if chlamydia positive.
- 366 • Feedback on testing rates provided every three months in the form of quantitative reports,
367 showing the GP's quarterly chlamydia testing rates over time.
- 368 • GP incentive payments: \$5 per eligible patient tested up to 20% of eligible patients tested;
369 \$7 per eligible patient tested for >20% to 40% of eligible patients tested; \$8 per eligible
370 patient tested for >40% of eligible patients tested. Payments will be made every three
371 months to the GP ordering the test.
- 372 • Practice nurse (PN) incentive payments: clinics will receive an additional \$10 payment per
373 test conducted if a PN discussed chlamydia testing with a patient and initiates a test. The

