515 **Repeat infection rates**

516 Repeat infection rates in eligible patients in intervention clusters only will be assessed as the number
517 of people with a positive repeat chlamydia test taken from 6 weeks to 6 months after an initial
518 positive test, as a proportion of all chlamydia positives at the initial visit. It will not be possible to
519 distinguish re-infection from an untreated partner from persistent infection following treatment
520 failure or acquisition of infection from a new partner, because samples tested in routine diagnostic
521 laboratories are not retained for genotyping.

522 ***Data collection***

523 ***GP characteristics***

524 GP characteristics will be collected via questionnaires and analysis of clinic consultation data prior to
525 commencement of the trial and will include demographics (age, sex, years worked as a GP);
526 education details (country of qualification, postgraduate qualifications); and knowledge, awareness,
527 attitudes and practices with respect to chlamydia testing and management. GPs' partner notification
528 practices and their familiarity with the clinical diagnostic features of PID will be assessed in the
529 questionnaire.

530 ***Patient characteristics***

531 Data from patients taking part in baseline and final prevalence surveys will be collected by self-
532 completed questionnaire using handheld computers. Data items include demographics (age, sex,
533 Aboriginal and/or Torres Strait Islander status, ethnic/cultural background, postcode of residence);
534 sexual behaviour data (proportion currently in a sexual relationship, number of sexual partners by
535 sex within last 3 and 12 months, number of new sexual partners in the last 12 months, duration of

536 most recent sexual partner, any concurrent or overlapping partnerships); presence of any symptoms
537 associated with chlamydia; and history of past chlamydia testing. The postcode of residence of
538 sexual partners will not be collected.

539 Minimal data including age, gender and whether ever had sex will be collected from all patients who
540 refuse to participate in the prevalence survey. These data will be used to assess non-response bias.

541 ***Chlamydia testing, diagnosis and sequelae data***

542 A data extraction tool (GRHANITE™, licensed by the University of Melbourne; www.grhanite.com)
543 will be installed on clinic computers where possible. This data extraction tool will provide ongoing

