624 rates of re-infection will be summarised by randomised group and compared using
625 appropriate hierarchical models.

626 ***Planned subgroup analyses***

627 The effect of the intervention within different subgroups of clusters will be explored, but interpreted
628 cautiously given the relatively small number of clusters. Subgroups may include sex, age group, area
629 type, Aboriginal and/or Torres Strait Islander status, estimated baseline chlamydia prevalence and
630 baseline testing rate. Intervention and control clusters will be compared within each subgroup and
631 evidence for heterogeneity of effects assessed using tests for interaction between randomised
632 intervention and subgroup. The effect of GP and clinic characteristics on testing uptake, annual
633 retesting rates, retesting after a positive diagnosis and chlamydia prevalence will be investigated.
634 The impact of patients attending from an area outside of the cluster will be investigated by analysing
635 patient postcode and its association with chlamydia prevalence.

636 ***Ethical issues***

637 ***Ethics committee approval***

638 The ACCEPt trial has been approved by the RACGP National Research and Evaluation Ethics
639 Committee and the University of Melbourne Human Research Ethics Committee. Approval has also
640 been obtained from the Aboriginal Health and Medical Research Council (AHMRC) Ethics Committee
641 to conduct the ACCEPt trial in AMSs. Specific services may also request ethical approval be sought
642 from local ethical committees.

643 ***Informed consent and information sheets***

644 ACCEPt research staff will explain the data collection requirements of the trial to all clinic staff prior
645 to them providing informed consent. Informed consent will cover all data collection activities of the
646 trial, recognise the principles of confidentiality and data ownership and define processes for
647 reporting of findings and release of trial results. A plain language participant information sheet will
648 be provided, which summarises the trial, participation requirements, confidentiality and disclosure
649 of information, and ethics approval and complaints contacts.

650 GPs can withdraw from the trial by notifying ACCEPt staff at any time and completing a withdrawal
651 of informed consent form. Unless otherwise requested, data collected from the clinic up until the

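### The repeat infection rate mixes retesting with repeat positivity, and the protocol both confines it to intervention clusters and lists it for comparison between arms

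*Protocol*

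**What the plan says.** Under Secondary endpoints, Repeat infection rates, the protocol sets the population and the start of the numerator: "Repeat infection rates in eligible patients in intervention clusters only will be assessed as the number". The numerator continues: "of people with a positive repeat chlamydia test taken from 6 weeks to 6 months after an initial" positive. The denominator follows: "as a proportion of all chlamydia positives at the initial visit". The one limitation given there is that re-infection from an untreated partner, treatment failure and infection from a new partner cannot be told apart. Incomplete retesting is not mentioned.

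The preceding endpoint, Test for repeat infection, covers retesting itself. It is measured in intervention and control clusters with the same window, and its numerator is the "number of individuals aged 16 to 29 years re-tested for chlamydia three months (allowable range six" weeks to six months) after a positive test.

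In Statistical tests, the last item of the outcome list groups testing uptake, testing coverage, the two retesting measures and re-infection. It says that "rates of re-infection will be summarised by randomised group and compared using" hierarchical models.

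Two other places bear on this. The intervention package includes a reminder system that recalls patients after "three months if chlamydia positive", whereas control clinics continue usual practice. The Rationale cites an audit of Australian general practices that "found that only 26.4% of 16–29-year-olds diagnosed with chlamydia" were retested within 1.5 to 4 months.

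**The concern.** There are two separate defects.

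The first is the denominator. Only people who come back for a test can enter the numerator, but everyone who was positive is in the denominator. The resulting figure moves when retesting moves, even if the chance of a positive repeat test does not. Reported alone as a repeat infection rate, it understates repeat infection by an amount that depends on how many people returned.

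The second is the contradiction over arms. An outcome defined in intervention clusters only cannot be compared between randomised groups. If the comparison were run anyway by applying the same definition to control clusters, the first defect would bias it, because recall after a positive test is part of the intervention. A higher rate in the intervention arm could then reflect recall alone, or a real fall in repeat positivity could be hidden.

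**Working it through.** The protocol gives no target, expected value or power for this endpoint, so there is no stated figure to reproduce. The check is an identity followed by an illustration.

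**Identity.** Let N be the initial positives, R those retested in the window and P those retested and positive.

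Rate as defined = P / N = (R / N) × (P / R) = share retested × positivity among the retested.

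R / N is close to the Test for repeat infection endpoint. The match is not exact, because that endpoint's denominator is unique individuals positive in the previous year.

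**Inputs**
- Share retested, 26.4%: the audit in the Rationale (2008–2009, window 1.5 to 4 months).
- Higher shares retested of 40%, 52.8% and 60%: assumptions, to represent the effect of recall.
- Positivity among the retested of 5%, 10% and 15%: assumptions.

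**Level.** At 26.4% retesting, 100% − 26.4% = 73.6% of the denominator cannot reach the numerator, so the rate cannot exceed 26.4%. With 10% positivity:

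| Share retested | Rate as defined | Positives / retested |
|---|---|---|
| 26.4% | 0.264 × 0.10 = 2.6% | 10% |
| 40% | 0.40 × 0.10 = 4.0% | 10% |
| 52.8% | 0.528 × 0.10 = 5.3% | 10% |
| 60% | 0.60 × 0.10 = 6.0% | 10% |
| 100% | 1.00 × 0.10 = 10% | 10% |

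**Sensitivity to positivity.** With retesting held at 26.4%, the rate as defined is 1.3%, 2.6% and 4.0% for positivity of 5%, 10% and 15%. It still tracks positivity when retesting is constant.

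**Between arms.** If positivity is equal in both arms, it cancels, and the ratio of rates equals the ratio of retesting shares:
- 40% against 26.4%: 0.40 / 0.264 = 1.52
- 52.8% against 26.4%: 0.528 / 0.264 = 2.00
- 60% against 26.4%: 0.60 / 0.264 = 2.27

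Conversely, the relative fall in positivity in the intervention arm that would leave the two rates equal is 1 − 0.264 / share retested, that is 34%, 50% and 56%.

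**The two sections side by side.** The endpoint definition says intervention clusters only; the outcome list says compared by randomised group. No other part of the protocol settles which applies.

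**The case against.** A fair defence has five parts.

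- **The specific definition should govern.** The endpoint text excludes control clusters, and the outcome list is loose: it also names testing coverage, for which no endpoint is defined. The list item may simply be a slip, in which case no biased comparison would be run. This is plausible and supports the simplest repair, but the protocol as written still says both things.
- **The retested share is already planned.** Test for repeat infection uses the same window in both arms, so a reader could roughly recover positivity among the retested by dividing one result by the other. This stands in part. The denominators are worded differently, and the protocol does not say that the two results will be read together.
- **The 26.4% does not describe this trial.** It comes from a pre-trial audit with a shorter window, whereas the endpoint runs to six months in clinics with active recall. This stands. A reader might infer from it that the trial would understate repeat infection by about 74%, but the documents do not support that figure. It would also require people not retested to have the same positivity as those retested.
- **Changing the denominator does not make the arms comparable.** Recalled patients in one arm and usual-care returners in the other may differ, in an unknown direction. The extraction tool is installed only where possible, and the backup pathology and Medicare data carry no unique patient code, so repeat tests cannot be linked to a first positive there. This stands and limits the fix.
- **The endpoint is minor.** It is not among the listed secondary objectives and has no hypothesis or power attached. This stands and sets the severity.

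**Conclusion.** The concern holds in a limited form. As defined, the rate is the product of retesting and repeat positivity. It is a lower bound on repeat infection, counted as any positive repeat test, whenever some initial positives are not retested. Separately, the endpoint definition and the outcome list contradict each other on whether arms are compared. If they were compared under this definition, recall alone would inflate the intervention arm, by a factor of 1.5 to 2.3 under the assumptions of equal positivity and retesting of 26.4% against 40% to 60%. The size is illustrative. The direction needs only that recall raises retesting.

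Two stronger readings are tempting and not supported:
- **That the rate measures retesting rather than re-infection.** It does not: at constant retesting it moves in proportion to positivity. Nor does the contradiction over arms cause the mixing; it only makes the mixing matter for inference.
- **That the trial would give false support to the hypothesis, raised in the background, that screening and treatment increase repeat infection.** No objective tests that hypothesis, and the endpoint definition does not provide for the between-arm comparison it would need.

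Severity: should-fix. The endpoint is secondary, and neither the primary outcome nor the sample size depends on it.

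**What to change.** 1. In Repeat infection rates, define repeat positivity as positives divided by people retested in the 6-week to 6-month window. Report it beside the share retested already planned under Test for repeat infection, using the same cohort of initial positives for both. If the current rate is also kept, label it a lower bound that depends on retesting.
2. Reconcile that section with Statistical tests. The simplest way is to remove re-infection from the outcomes compared by randomised group and keep it descriptive in intervention clusters.
3. If both arms are reported instead, limit this to clinics with linked extraction data. State that those retested are a selected group whose make-up may differ between arms, so that a difference is not read as an effect on re-infection.

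The first two steps change wording only and need no new data. The cost is a smaller denominator and a result that describes people who returned rather than everyone who was positive. The third step also costs coverage, because clinics without linked data drop out.
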